7.1 Safety Analysis Set

The safety analysis set will consist of all subjects who receive IP (AMG 334 or placebo). Subjects will be analyzed according to the IP received (AMG 334 or Placebo).

7.2 Pharmacokinetic (PK) Analysis Set

The PK analysis set will contain all subjects who receive IP and have at least one PK concentration result.

Statistical Analysis Plan: 20140207

Date: 17 May 2017 Page 17

8. Interim Analysis and Early Stopping Guidelines

8.1 Dose Level Review Meetings and Safety Review Meetings

The DLRM members will be composed of the PI, Amgen MM, Amgen GSO or designee, Early Development Leader or designee, Clinical Study Manager or designee, and Biostatistics representative or designee. Additional members may be added as needed (eg, PK Scientist). The Safety Review Meeting members include the PI, Amgen MM, and Amgen GSO or designee. The DLRM and Safety Review Meeting voting members will include the PI, Amgen MM, and Amgen GSO or designee.

A Safety Review Meeting will be held after PACAP-38 dosing has been completed in each cohort in Part A. Available vital signs and AE occurring at least 24 hours following PACAP-38 dosing for each cohort will be reviewed by the Safety Review Meeting members to decide enrollment in subsequent cohort. If the Safety Review Meeting members decide not to proceed with enrollment in subsequent cohort, then a Safety Review Meeting or DLRM will be held after the last dosed cohort. Unscheduled DLRMs can be called at any time by any of the DLRM voting members.

The Safety Review Meeting and DLRM voting members will decide whether or not to proceed with enrollment in the Randomization (AMG 334 or Placebo) Phase and if the decision is to proceed with enrollment in the Randomization (AMG 334 or Placebo) Phase, the Safety Review Meeting and DLRM voting members will select a PACAP-38 dose. The maximum dose of PACAP-38 will not exceed 115 pmol/kg. At any time the Safety Review Meeting members may decide to add additional Non Randomized (PACAP-38 Only) Dose Selection Subjects pending review of emerging safety, and/or tolerability data. A future modification of the PACAP-38 dose may occur based on emerging safety, and/or tolerability findings.

All available study data, including the headache questionnaires, demographics, IP administration, medical history, concomitant medications, AE (including MLA), ECGs, vital signs, and laboratory results will be reviewed. Data to be reviewed at the Safety Review Meeting and DLRMs during the PACAP-38 Dose Selection Phase will not be blinded. Data to be reviewed for any unscheduled DLRM post the PACAP-38 Dose Selection Phase will be reviewed blinded (ie., treatment assignment will not be revealed) unless unblinding is deemed necessary for the review team to make dosing decisions. If deemed necessary, unblinding will be performed to assist dose decisions in accordance with Amgen standard procedures.

Statistical Analysis Plan: 20140207

Date: 17 May 2017 Page 18

8.2 Interim Analysis

Once 24 hours of data is collected from 16 PACAP-38 responders dosed with AMG 334 or Placebo (8 per group) after PACAP-38 infusion on Day 8, an interim analysis will be performed to determine if the challenge-agent, PACAP-38, invokes historical rates of MLA (~66%) and if AMG 334 has greater efficacy than placebo. If the number of MLAs does not meet historical rates, AMG 334 does not appear to be better at blocking PACAP-38 induced migraines compared with placebo, or AMG 334 appears to be sufficiently better at blocking PACAP-38 induced migraines compared with placebo, the study will be terminated (see below for more details). Otherwise, another 20 PACAP-38 responders will be randomized. Appropriate decision rules, outlined below were developed to determine whether to increase the sample size (another 20 responders dosed with AMG 334 or Placebo, 10 per treatment group) or to stop, either due to demonstration of treatment effect or treatment utility.

Decision rules to be applied during the trial are:

- At the interim analysis, if 3 or less of the 8 placebo subjects have a MLA, randomization will be stopped and it will be concluded that PACAP-38 does not induce a sufficient proportion of MLA for the study to test the hypothesis.
- 2. At the interim analysis, if 4 or more placebo subjects have a MLA, yet more subjects receiving AMG 334 have MLA than placebo subjects, then randomization will be stopped and it will be concluded that AMG 334 is ineffective in blocking PACAP-38 induced MLA.
- 3. If the difference at the interim analysis in the proportion of subjects with MLA (placebo-AMG 334) is greater than or equal to 75% then randomization will be stopped and it will be concluded that AMG 334 is effective in blocking PACAP-38 induced MLA.
- 4. If none of the first 3 decision rules apply at the interim analysis, an additional 20 subjects will be randomized in the trial. At the end of trial, if the p-value from the one-sided Fisher's Exact test is less than 0.1, it will be concluded that AMG 334 is effective in blocking MLA (TRIAL SUCCESS –LATE), or if the p-value from the one-sided Fishers Exact test is greater than or equal to 0.1, it will be concluded that AMG 334 is ineffective at blocking MLA.

The results from 10,000 simulated trials demonstrating the probability of failing at the interim analysis, as well as the probability of overall trial result, for different potential scenarios of the proportion of subjects with MLA in each treatment group are shown below:

Statistical Analysis Plan: 20140207

Date: 17 May 2017 Page 19

Probability of Fail at the Interim Analysis:

Placebo subjects with MLA

		70%	50%	35%	20%
	20%	6%	36%	72%	95%
AMG 334 subjects with MLA	35%	8%	40%	73%	
AIVIO 334 Subjects With MEA	50%	15%	50%		
	70%	40%			

Probability of Overall Trial Success:

Placebo subjects with MLA

20%	35%	50%	70%		
1%	14% 4%	48% 23% 6%	91% 72% 38% 5%	20% 35% 50% 70%	AMG 334 subjects with MLA

From the above, it can be seen that, if PACAP-38 does not induce MLA in a sufficient proportion of subjects for the study to test the hypothesis, or AMG 334 appears to be ineffective in blocking PACAP-38 induced MLA, the trial is more likely to fail at the interim analysis stage (the bold and underlined in the results with respect to the probability of fail at the interim analysis). However, should the study continue from the interim analysis stage, even by chance, the overall type I error is controlled such that the study is highly unlikely to conclude AMG 334 is effective in blocking PACAP-38 induced MLA (overall trial success) when it is not (the bold and underlined in the results with respect to the probability of overall trial success).

Designated personnel from Biostatistics will be unblinded for the interim analysis. After interim analysis, the designated unblinded Biostatistics personnel will recommend to the study team whether the sample size remains at 8 per group or needs to be increased to 18 per group.

Statistical Analysis Plan: 20140207

Date: 17 May 2017 Page 20

9. Data Screening and Acceptance

9.1 General Principles

The objective of the data screening is to assess the quantity, quality and statistical characteristics of the data relative to the requirements of the planned analyses.

9.2 Data Handling and Electronic Transfer of Data

The Amgen Global Study Operations-Data Management (GSO-DM) department will provide all data to be used in the planned analyses. This study will use the RAVE database.

Details of PK, Antibody, and external lab data transfer to the data base is provided in the corresponding study data transfer plans. See Data Management Plan (DMP).

9.3 Handling of Missing and Incomplete Data Imputation Rules for Partial or Missing Start Dates

	Missing	Imputation	Exception
Start date (AE, concomitant medication)	Day	01	Default to Study Day 1 if an adverse event starts the same year and month as Study Day 1 and the flag indicates that the adverse event started on or after the first dose on the Adverse Events eCRF
	Day/Month	01JAN	Default to Study Day 1 if an event started the same year as Study Day 1 and the flag indicates that the adverse event started on or after the first dose on the Adverse Events eCRF
	Day/Month/Year	No imputation	

Imputation Rules for Partial or Missing Stop Dates

If the month and year are present, impute the last day of the month. If only the year is present, impute December 31 of that year. If the stop date is entirely missing, assume

Statistical Analysis Plan: 20140207

Date: 17 May 2017 Page 21

the event or medication is ongoing. If a partial or complete stop date is present and the 'ongoing' or 'continuing' box is checked, then it will be assumed that the AE or conmed stopped and the stop date will be imputed, if partial. Ensure the imputed stop date is on or after the complete or imputed start date.

9.4 Detection of Bias

Lack of protocol compliance and the potential for biased statistical analyses will be examined by assessing the incidence of important protocol deviations (IPD) in each treatment group. The clinical study team will identify and document the criteria for IPD.

9.5 Outliers

All confirmed outlier data will be included in the analyses presented in this SAP unless there is sufficient scientific justification (eg, IPD leading to invalid data) to exclude them.

PK concentration data will be evaluated for outliers by visual inspection and decisions to re-assay individual samples will be made in accordance with standard Pharmacokinetics and Drug Metabolism (PKDM) practice. All excluded observations will be detailed by PKDM along with reasons for exclusion, in accordance with standard PKDM practices.

9.6 Distributional Characteristics

Where appropriate, the assumptions underlying the proposed statistical methodologies will be assessed. If required data transformations or alternative non-parametric methods of analyses will be utilized.

9.7 Validation of Statistical Analyses

Programs will be developed and maintained, and output will be verified in accordance with current risk-based quality control procedures.

Tables, figures and listings (TFL) will be produced with validated standard macro programs where standard macros can produce the specified outputs.

The production environment for statistical analyses consists of Amgen-supported versions of statistical analysis software, for example the SAS System version 9.4 or later.

Additional statistical software may be used to perform exploratory/ad-hoc analyses.

10. Statistical Methods of Analysis

10.1 General Principles

Unless otherwise stated, data from PACAP-38 responders who go on to be randomized and receive IP will be summarized. Data from PACAP-38 non-responders, and data from

Statistical Analysis Plan: 20140207

Date: 17 May 2017 Page 22

PACAP-38 responders that do not receive IP, will not be included in the summaries, but will be reviewed.

Unless otherwise specified, data will be summarized using the safety analysis set, by actual treatment group (AMG 334 or Placebo).

Descriptive statistics will be provided for selected demographics, safety and PK data. Descriptive statistics on continuous measurements will include means, medians, standard deviations (and standard errors for post-baseline data), quartiles, and ranges, while categorical data will be summarized using frequency counts and percentages. Where statistical models are applied to the data, estimates of the differences/ratios, confidence intervals and corresponding p-values will be presented, as applicable. However, these are for descriptive and illustrative purposes only and to aid interpretation of the data; no formal statistical hypothesis testing will be performed.

When data are summarized by time, the values recorded against the scheduled time points, including any time windows specified in the protocol will be used.

When assessing minimum/maximum increases or decreases over the study, all assessments, including unscheduled assessments will be used.

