6.2 Investigational Product

All investigational products will be administered at the research facility by a qualified staff member. A physician must be present at the time of Investigational Product administration.

6.2.1 Amgen Investigational Product AMG 334

AMG 334 will be manufactured and packaged by Amgen Inc. and distributed using Amgen clinical study drug distribution procedures.

Active AMG 334 will be packaged in open label 5 mL clear glass vials containing 1 mL of 70 mg/mL AMG 334 formulated with mM sodium acetate, $\mathbf{v} \otimes \mathbf{w} \otimes \mathbf{w}$, sucrose, $\mathbf{v} \otimes \mathbf{w} \otimes \mathbf{w}$

All AMG 334 and matching placebo supplies will be shipped to the study site frozen and should be stored at CC °C to CCI C in a non frost-free freezer until ready to use.

For more information regarding investigational product handling and preparation please see the study specific IPIM which is provided as a separate document.

6.2.1.1 Dosage, Administration, and Schedule for AMG 334

Single doses of AMG 334 up to 210 mg SC or 140 mg IV were found to be generally well tolerated in both healthy subjects and migraine subjects (FIH Study 20101267). While the AMG 334 exposure and its migraine prevention efficacy relationship is to be established, a high dose of AMG 334 (140 mg intravenous, IV) is selected for this study in order to provide maximum CGRP receptor blockade against the PACAP-38 challenge.

After a single IV administration of AMG 334 at 140 mg, the distribution phase of serum AMG 334 was approximately completed by Day 8 (20101267, Figure 1). The mean serum AMG 334 concentration on Day 8 was 15.4 μ g/mL, which is similar to the C_{avg} (15.9 ug/mL) of AMG 334 after the third 140 mg SC monthly dose administration. Monthly SC 140 mg administration is one of the higher dose regimens currently being evaluated in Phase 2 migraine clinical trials. Based on this information, Day 8 is considered as an appropriate time point to provide similar target coverage as in AMG 334 Phase 2 migraine clinical trials coverage and thus is selected for PACAP-38 challenge.

IV route is being chosen over subcutaneous (SC) as it is the faster route to achieve the target concentration after AMG 334 administration.

Figure 1. Mean (+SD) Serum AMG 334 Concentration-time Profiles After Intravenous Administration of AMG 334 at 140 mg

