10.1.2 Analysis Sets

10.1.2.1 Safety Analysis Set

The safety analysis set will consist of all subjects who receive investigational product and PACAP-38. Subjects will be analyzed according to the treatment received (AMG334 or Placebo).

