10.5 Planned Methods of Analysis

10.5.1 General Considerations

Descriptive statistics will be provided for selected demographic, safety and PK data. Descriptive statistics on continuous measurements will include means, medians, standard deviations, and ranges, while categorical data will be summarized using frequency counts and percentages. Comparison of PACAP-38 ability to produce MLA between AMG 344 and placebo will be done with Fisher's Exact Test. Unless otherwise specified, data will be summarized using the safety analysis set, by actual treatment group. If a subject receives IP, but does not receive PACAP-38, their data will be listed only; their data will not be included in any summaries or analyses.

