10.5 Primary Endpoint Planned Analysis

The number and percent of subjects experiencing a MLA within 24 hours after PACAP-38 infusion will be summarized for each treatment group. Comparison of PACAP-38 ability to produce MLA between AMG 334 and placebo will be done using the Fisher's Exact test.

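### The primary and headache tests are grouped by treatment received, and no as-randomised analysis is defined, so a single misdosed subject could change the conclusion

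*SAP*

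**What the plan says.** SAP 10.1 (General Principles) gives the default: where a section does not say otherwise, summaries use the safety analysis set, "by actual treatment group (AMG 334 or Placebo"). SAP 7.1 defines that set's grouping: "Subjects will be analyzed according to the IP received (AMG 334 or Placebo"). The protocol agrees. Section 10.1.2.1 says "Subjects will be analyzed according to the treatment received (AMG334 or Placebo"), and section 10.5.1 says that, unless otherwise specified, "data will be summarized using the safety analysis set, by actual treatment group".

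The primary analysis in SAP 10.5 says only that "Comparison of PACAP-38 ability to produce MLA between AMG 334 and placebo will be done using the Fisher's Exact test". It names no analysis set, and the headache test in SAP 10.6.1 is worded in the same way. The only other set in either document is the pharmacokinetic (PK) set.

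SAP 8.2 names no set for the interim rules. For the end of the trial it states that "if the p-value from the one-sided Fisher's Exact test is less than 0.1, it will be concluded that AMG 334 is effective" in blocking MLA.

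**The concern.** Part B is a randomised, double-blind comparison, and SAP 8.2 attaches a conclusion to its p-value. Randomisation makes the groups comparable as assigned. Grouping by product received is conventional for safety and PK, but for efficacy it gives up that protection as soon as one subject receives the wrong product. Neither document says that this grouping was chosen for efficacy; it arrives through a general default.

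Three things are at stake if a misdose occurs:

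- The final p < 0.1 conclusion can change with the regrouping of one subject.
- The interim rule of a 75-point difference can change in the same way.
- An unbalanced misdose among the first 16 subjects turns 8 v 8 into 7 v 9. Interim rule 1 counts MLAs out of exactly 8 placebo subjects and gives no threshold for 7 or 9.

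A mix-up is possible but not shown to be likely. Protocol 6.2.1 states that "Active AMG 334 will be packaged in open label 5 mL clear glass vials", and protocol 3.4 and 5.1 give replacement subjects the treatment of the person replaced, through an unblinded pharmacist who holds the list.

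**Working it through.** **Inputs.** From SAP 3.2 and 8.2: 8 per arm at the interim, 10 more per arm afterwards (18 in total), and planning MLA rates of 70% (placebo) and 20% (AMG 334). The SAP 8.2 rules are:

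1. stop if 3 or fewer of the 8 placebo subjects have an MLA;
2. stop if more AMG 334 than placebo subjects have an MLA;
3. stop for success if the difference is at least 75 points;
4. otherwise continue, and declare success if one-sided Fisher p < 0.1.

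The number of misdosed subjects is not in the documents. Zero to two swapped pairs is an assumption.

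**Step 1: reproduce the plan's figure.** P(success) = Σ P(stage-1 counts) × [1 if rule 3 applies; 0 if rule 1 or 2 applies; otherwise P(Fisher p < 0.1 on the pooled 18 v 18)], with binomial counts. At 70% v 20% this gives 0.1952 (early) + 0.7144 (late) = 0.9095 after rounding, against the stated figure of about 91%. At 70% v 70% it gives 0.0523, against the stated 5%.

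**Step 2: no misdosing.** Randomised arm and product received coincide for every subject, so both groupings give 0.9095 and 0.0523.

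**Step 3: can one subject change the conclusion?** One-sided Fisher p is the hypergeometric probability of at least the observed number of placebo MLAs, given the total. In each row one subject randomised to placebo received AMG 334.

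| As randomised (placebo v AMG 334) | p | Regrouped by product received | p |
|---|---|---|---|
| 10/18 v 5/18 | 0.088 (success) | subject had an MLA: 9/17 v 6/19 | 0.169 (failure) |
| 9/18 v 5/18 | 0.153 (failure) | subject had no MLA: 9/17 v 5/19 | 0.098 (success) |

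At the interim, 6/8 v 0/8 is 75 points and stops for success. Regrouping one placebo subject with an MLA gives 5/7 − 1/9 = 71.4 − 11.1 = 60.3 points, and the trial continues.

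**Step 4: type I error under as-treated grouping, one stage-2 misdose.**

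| Null rate | Nature of the error | As-treated type I error |
|---|---|---|
| 70% | none | 5.2% |
| 70% | unrelated to outcome | 4.9% or 6.6%, by direction |
| 70% | misdosed subject's outcome fixed in the direction favouring AMG 334 | 7.4% or 7.8%, by direction |
| 50% | same | 8.0% |

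**Step 5: what as-randomised grouping costs.** Success probability at 70% v 20%:

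| Misdosing assumed | As randomised | As treated |
|---|---|---|
| none | 91.0% | 91.0% |
| one subject, stage 2 | 89.4–89.5% | 90.7–91.2% |
| one swapped pair, stage 1 | 83.3% | 91.0% |
| one swapped pair, stage 2 | 87.3% | 91.0% |
| one swapped pair in each stage | 77.6% | 91.0% |

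**The case against.** The best defence is that this is a single-dose mechanistic study. Protocol 2.5 asks whether CGRP lies downstream of PACAP-38, and a subject who received the other product does not inform the effect of the assigned one. Grouping by product received avoids dilution, and step 5 shows that this is worth something. SAP 8.2 also describes the interim subjects by what they were dosed with, so its wording is compatible with the default. A Fisher test does not need equal arms. Important protocol deviations are reviewed by treatment group for possible bias (SAP 9.4), so a recorded misdose would be open to scrutiny. All of this stands. It justifies reporting an as-treated analysis, but not leaving it as the only one.

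Two stronger readings are tempting and are not supported. A reader might infer that any dosing error invalidates the comparison. An error unrelated to outcome changes group sizes but introduces no selection, and step 4 stays below 10% throughout. A reader might also infer from the open-label vials and the replacement procedure that misdosing is likely. The documents report none, place preparation details in a separate manual that is not available here, and do not say that replacement treatments are assigned by hand. The item assigned manually in protocol section 5 is the subject identification number.

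SAP 10.1 also calls model-based p-values descriptive. That sits awkwardly beside the decision rule in SAP 8.2, but does not alter which subjects are counted in which arm.

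**Conclusion.** The point holds at low severity. By default, the randomised primary and headache comparisons are grouped by product received, and no as-randomised alternative is planned. The effect is nil if dosing is correct. If it is not, one regrouped subject can move the result across p = 0.1 in either direction or undo an interim success, and an unbalanced stage-1 misdose leaves rule 1 without its stated denominator. The step 3 examples are results near the boundary, chosen to show what is possible; they are not expected effects. The step 4 and 5 figures rest on the SAP's own rates, binomial outcomes and the assumed misdosing. The claim is not that the present plan inflates the error rate materially. It is that the grouping for efficacy should be stated and fixed before results are seen.

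**What to change.** Add to SAP 7 an efficacy analysis set: all subjects randomised, dosed with AMG 334 or placebo, and challenged with PACAP-38 after that dose, analysed by randomised arm. Name it in SAP 8.2, 10.5, 10.6.1 and 10.7.1 to 10.7.3. Keep treatment received for safety and PK, and report the as-treated MLA and headache comparisons as sensitivity analyses. State in SAP 8.2 that the interim rules count by randomised arm, which stops a misdose from changing rule 1's denominator of 8.

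The set would still omit randomised subjects who are not dosed or not challenged. SAP 10.1 and 11 already leave them out of the summaries, and protocol 3.4 allows those lost before PACAP-38 to be replaced. That departure from a full as-randomised analysis needs no dosing error to operate. It should be disclosed, with numbers and reasons by arm.

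The cost is one definition and a few cross-references, with no new data and no change to the design's operating characteristics when dosing is correct. The drawback is the dilution in step 5, which arises only after a misdose.
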